7.3.4 Adverse Event Reporting to Country Regulatory Authorities by the Sponsor

The Sponsor will report SAEs and reportable device deficiencies/malfunctions to the country regulatory authority, per local requirements.

Note: Reportable device deficiencies/malfunctions include device deficiencies/malfunctions that might have led to an SAE if a) suitable action had not been taken or b) intervention had not been made or c) if circumstances had been less fortunate. These are handled under the SAE reporting system.

8.0 STATISTICAL CONSIDERATIONS

8.1 Analysis Population

8.2 Statistical Analyses

Descriptive analyses will be performed for subject baseline characteristics, procedural characteristics, and all endpoints.

8.3 Sample Size

Study Name: Perclose Multi-Access DUS Trial

Clinical Investigation Plan

The sample size of 35 patients

Subjects who will be treated with 2 Perclose SMC for closure of access sites > 8F.

A minimum of 8 subjects will be enrolled.

Subjects who will have 3 or 4 access sites per vein

enrolling 12 subjects is expected.

8.4 Timing of Analysis

The primary analysis will be performed after database lock when all subjects have completed their 30-day follow-up visit.

8.5 Subgroup Analysis

Abbott will have a subgroup analysis by:

- Number of access site per a subject
- Number of access site per a vein
- > 8F vs ≤ 8F
- Female vs Male
- Age ≥ 65 vs < 65
- Race/Ethnicity
- Diabetes

8.6 Multiplicity

Since no hypothesis testing is planned, no adjustment will be made for multiple testing.

8.7 Success Criteria

No success criterion is applied in this clinical investigation.

8.8 Deviations from Statistical Plan

Any major changes to the statistical plan will be documented in an amendment to the statistical analysis plan. Less significant changes to the planned analyses will be documented in the final report.

8.9 Statistical Criteria for Termination

There are no statistical criteria for the termination of this clinical investigation.

9.0 DIRECT ACCESS TO SOURCE DATA/DOCUMENTS

The investigator/institution will permit direct access to source data/documents for the purpose of performing clinical investigation-related monitoring, audits, IRB review, and regulatory inspections.

Subjects providing informed consent are agreeing to allow clinical investigation monitors or regulatory authorities, including foreign countries, to review, in confidence, any records identifying the subjects in this clinical investigation. This information may be shared with regulatory agencies; however, Sponsor undertakes not to otherwise release the subject's personal and private information.

10.0 QUALITY CONTROL AND QUALITY ASSURANCE

10.1 Selection of Clinical Sites and Investigators

The Sponsor will select investigators qualified by training and experience to participate in the clinical investigation. Sites will be selected based upon a review of a recent site assessment, if applicable, and the qualifications of the investigators who will participate in the clinical investigation.

10.2 Clinical Investigation Finances and Agreements

The clinical investigation will be financed by Abbott. Investigational sites will be compensated by Abbott for participation in the clinical investigation per the conditions of agreement between the Sponsor and the Investigational site.

10.3 CIP Amendments

Approved CIP amendments will be provided to the Investigators by the Sponsor prior to implementing the amendment. The Principal Investigator is responsible for notifying the IRB or equivalent committee of the CIP amendment (administrative changes) or obtaining IRB's approval of the CIP amendment (changes in subject care or safety), according to the instructions provided by the Sponsor with the CIP amendment.

Acknowledgement/approval by the IRB of the CIP amendment must be documented in writing prior to implementation of the CIP amendment. Copies of this documentation must also be provided to the Sponsor.

10.4 Training

10.4.1 Site Training

All Investigators and clinical investigation personnel are required to attend Sponsor training sessions, which may be conducted at an Investigator's meeting, a site initiation visit, or other appropriate training sessions. Over-the-phone or self-training may take place as required. Training of Investigators and clinical investigation personnel will include but is not limited to, the CIP requirements, electronic case report form completion, and clinical investigation personnel responsibilities. All Investigators and clinical investigation personnel that are trained must sign a training log (or an equivalent) upon completion of the training.

10.5 Monitoring

Sponsor and/or designee will monitor the clinical investigation over its duration according to the CIP-specific monitoring plan, which will include the planned extent of source data verification.

Prior to initiating any procedure, the Sponsor monitor (or delegate) will ensure that the following criteria are met:

- The investigator understands and accepts the obligation to conduct the clinical investigation according to the protocol and applicable regulations, and has signed the Investigator Agreement.
- The Investigator and his/her staff should have sufficient time and facilities to conduct the clinical investigation and should have access to an adequate number of appropriate subjects to conduct the clinical investigation.
- Source documentation (including original medical records) must be available to substantiate proper informed consent procedures, adherence to protocol procedures, adequate reporting and follow-up of adverse events, accuracy of data collected on case report forms, and device information.
- The Investigator/site will permit access to such records. A monitoring visit sign-in log will be maintained at the site. The Investigator will agree to dedicate an adequate amount of time to the monitoring process. The Investigator and/or research coordinator will be available for monitoring visits. It is expected that the Investigator will provide the monitor with a suitable working environment for review of clinical investigation-related documents.

10.6 Deviations from CIP

The Investigator should not deviate from the protocol for any reason except in cases of medical emergencies when the deviation is necessary to protect the rights, safety, and well-being of the subject or eliminate an apparent immediate hazard to the subject. In that event, the Investigator will notify Sponsor immediately by phone or in writing.

No waivers for protocol deviations will be granted by the Sponsor. All deviations must be reported to the Sponsor using the Deviation CRF. The occurrence of protocol deviations will be monitored by the Sponsor for evaluation of investigator compliance to the protocol and regulatory requirements and dealt with according to written procedures. Investigators will inform their IRB or equivalent committee of all protocol deviations in accordance with their specific IRB or equivalent committee reporting policies and procedures.

In the event of repeated non-compliance, as determined by the Sponsor, a Sponsor's monitor or company representative will attempt to secure compliance by one or more of the following (and not limited to):

- Visiting the investigator and/or delegate
- Telephoning the investigator and/or delegate
- Corresponding with the investigator and/or delegate

Repeated non-compliance with the signed agreement, the protocol, or any other conditions of the clinical investigation may result in further escalation in accordance with the Sponsor's written procedures, including securing compliance or, at its sole discretion, Sponsor may terminate the investigator's participation in the clinical investigation.

10.7 Quality Assurance Audit

A Sponsor representative or designee may request access to all clinical investigation records, including source documentation, for inspection during a Quality Assurance audit.

If an investigator is contacted by a Regulatory Agency in relation to this clinical investigation, the Investigator will notify Sponsor immediately. The Investigator and Research Coordinator must be available to respond to reasonable requests and audit queries made during the audit process. The Investigator must provide the Sponsor with copies of all correspondence that may affect the review of the current clinical investigation (e.g., Form FDA 483, Inspectional Observations, Warning Letters, Inspection Reports, etc.). The Sponsor may provide any needed assistance in responding to regulatory audits.

10.8 Clinical Events Committee (CEC)

The CEC is an independent adjudication body comprised of qualified physicians who are not participants in the clinical investigation. The CEC will review and adjudicate pre-specified vascular complications and other access site-related complications (endpoint events described in Section 4.2) reported by investigators or identified by Safety personnel for the clinical

investigation as defined in the CEC charter and according to definitions provided in this CIP and relations (closure procedure related, SMC related) will also be determined.

11.0 DATA HANDLING AND RECORD KEEPING

Sponsor and/or its affiliates will maintain documentation of the systems and procedures used in data collection for the duration of the clinical investigation.

CRF data collection will be performed through a secure web portal, and only authorized personnel will access the Electronic Data Capture (EDC) system using a unique username and password to enter, review, or correct data. Passwords and electronic signatures will be strictly confidential.

The data will be subjected to consistency and validation checks within the EDC system and supplemental review by the Sponsor.

At the conclusion of the clinical investigation, completed CRF images with the date-and-time stamped electronic audit trail indicating the user, the data entered, and any reason for change will be provided to the investigational sites.

For the duration of the clinical investigation, the Investigator will maintain complete and accurate documentation including, but not limited to, medical records, clinical investigation progress records, laboratory reports, CRFs, signed ICFs, correspondence with the IRB, and clinical investigation monitor/Sponsor, adverse event reports, and information regarding subject discontinuation or completion of the clinical investigation.

11.1 Protection of Personally Identifiable Information

The Sponsor respects and protects personally identifiable information collected or maintained for this clinical investigation.

The Sponsor implements technical and physical access controls to ensure that Personal Information is accessible only to and processed only on a 'need to know' basis, including periodic review of access rights, and revocation of access when an individual's employment is terminated or the individual transitions to a role that does not require access to Personal Information, and appropriate restrictions on physical access to premises, facilities, equipment, and records containing Personal Information.

The Sponsor requires the investigational sites to enter only pseudonymous Personal Information (key-coded) necessary to conduct the Clinical Investigation, such as the subject's medical condition, treatment, dates of treatment, etc., into Sponsor's data management systems. The Sponsor discloses as part of the clinical investigation informed consent process that some Sponsor representatives still may see Personal Information at the participating sites for technical support of the participating physicians on the device implant or procedures, monitoring, and quality control purposes. All parties will observe confidentiality of Personal

Information always throughout the clinical investigation. All reports and data publications will preserve the privacy of each subject and confidentiality of his/her information.

The Sponsor data management systems and processes were designed, developed, and tested according to industry standards to appropriately safeguard Confidential Information (including any Personal Information) against unauthorized access and/or interference by third parties, intrusion, theft, destruction, loss, or alteration. Clinical Investigation data are encrypted in transit and at rest.

The Sponsor maintains a Privacy Incident procedure that complies in all respects with Applicable Law and industry best practices.

11.2 Data Management Plan

A Data Management Plan (DMP) will describe procedures used for data review, data cleaning, and issuing and resolving data discrepancies. If appropriate, the DMP may be updated throughout the duration of the clinical investigation. All revisions will be tracked and document controlled.

11.3 Source Documentation

Abbott requires the Investigator to maintain information in the subject's original medical records that corroborates data collected on the CRFs. The following information should be included in the subject record at a minimum and if applicable to the clinical investigation:

- Medical history/physical condition of the subject before involvement in the clinical investigation sufficient to verify protocol entry criteria
- Dated and signed notes on the day of entry into the clinical investigation referencing the Sponsor, protocol number, subject ID number, and a statement that informed consent was obtained
- Dated and signed notes from each subject visit (for specific results of procedures and exams)
- Adverse events reported and their resolution, including supporting documents, such as discharge summaries, catheterization laboratory reports, ECGs, and lab results, including documentation of site awareness of SAEs and of investigator assessment of device relationship for SAEs.
- Notes regarding medications taken during the clinical investigation (including start and stop dates)
- Subject's condition upon completion of or withdrawal from the clinical investigation
- Any other data required to substantiate data entered into the CRF

11.4 Electronic Case Report Form Completion

Primary data collection based on source-documented hospital and/or clinic chart reviews will be performed clearly and accurately by site personnel trained on the protocol and eCRF completion. The investigator will ensure accuracy, completeness, legibility, and timeliness of the data reported to the Sponsor on the eCRFs and in all required reports. eCRF data will be collected for all subjects that are registered in the trial.

Only authorized site personnel will be permitted to enter the eCRF data through the EDC system deployed by the Sponsor. An electronic audit trail will be used to track any subsequent changes of the entered data.

11.5 Record Retention

The Sponsor and Investigator/Site will archive and retain all documents pertaining to the clinical investigation as per the applicable regulatory record retention requirements. The Investigator must obtain permission from Sponsor in writing before destroying or transferring control of any clinical investigation records.

12.0 ETHICAL CONSIDERATION

12.1 Institutional Review Board Approval

Institutional Review Board (IRB) approval for the protocol and ICF/other written information provided to the subject will be obtained by the Principal Investigator at each investigational site prior to consenting and registering subjects in this clinical investigation. The approval letter must be received prior to the start of this clinical investigation and a copy must be provided to the Sponsor.

Any amendments to the protocol as well as associated ICF changes will be submitted to the IRB/EC/Competent Authority and written approval obtained prior to implementation, according to each institution's IRB requirements.

No changes will be made to the protocol or ICF or other written information provided to the subject without appropriate approvals, including IRB, the Sponsor, and the regulatory agencies (if applicable).

Until the clinical investigation is completed, the Investigator will advise his/her IRB of the progress of this clinical investigation, per IRB requirements. Written approval must be obtained from the IRB yearly to continue the clinical investigation, or according to each institution's IRB requirements.

No investigative procedures other than those defined in this protocol will be undertaken on the registered subjects without the written agreement of the IRB and the Sponsor.

13.0 CLINICAL INVESTIGATION COMPLETION

The clinical investigation will end when the last visit of the last subject registered has been completed.

The clinical investigation will be concluded when:

- All sites are closed AND
- The final report has been provided to investigators, or the Sponsor has provided formal documentation of clinical investigation closure.

The final clinical investigation report will be submitted within one year of the end of the investigation.

14.0 PUBLICATION POLICY

The data and results from the clinical investigation are the sole property of the Sponsor. The Sponsor shall have the right to access and use all data and results generated during the clinical investigation. The Investigators will not use this clinical investigation-related data without the written consent of the Sponsor for any purpose other than for clinical investigation completion or for generation of publication materials, as referenced in the Clinical Trial Agreement. Single-center results are not allowed to be published or presented before the multi-center results. Any proposals for publications or presentations by the investigators must be reviewed and approved by the Sponsor in a timely manner to enable Sponsor review in compliance with the Sponsor's publication policy set forth in the Clinical Trial Agreement.

Upon receiving IDE approval from the FDA, the Sponsor will be responsible for registering this clinical investigation on the ClinicalTrials.gov website, in accordance with the International Committee of Medical Journal Editors guidelines, or any other applicable guidelines. Sponsor shall be responsible for any such registration and results posting as required by the ClinicalTrials.gov website. Institution and/or Principal Investigator(s) shall not take any action to register the clinical investigation. A full report of the pre-specified outcomes, regardless of the results, will be made public through the ClinicalTrials.gov website no later than 12 months after clinical investigation completion, as required by section 801 of the FDA Amendments Act. If this clinical investigation is terminated early, the Sponsor will make every effort to hasten the release of the pre-specified outcomes through the ClinicalTrials.gov website.

15.0 RISK ANALYSIS

This clinical study is designed to confirm the frequency of asymptomatic/non-visible vascular complication possibly related to Perclose SMC by femoral DUS at discharge and 30 days.

This study follows site standard practice of ablation and vessel closure procedures and discharge, and the 30-day DUS (if complications are observed at discharge DUS) is the only study-specific requirement.

Although "scheduled" femoral DUS is not a routine practice after the catheterization procedure, it is used for further confirmation of symptomatic or suspected vascular complications as the standard practice. Femoral DUS is a non-invasive modality and no additional risks are expected. Therefore, this study is a non-significant risk study.

—

REFERENCES:

1. Mahadevan, V.S., et al., *Pre-closure of femoral venous access sites used for large-sized sheath insertion with the Perclose device in adults undergoing cardiac intervention.* Heart, 2008. **94**(5): p. 571-2.

2. Hamid, T., et al., *Preclosure of large-sized venous access sites in adults undergoing transcatheter structural interventions*. Catheter Cardiovasc Interv, 2013. **81**(4): p. 586-90.

3. Mohanty, S., et al., *Venous access-site closure with vascular closure device vs. manual compression in patients undergoing catheter ablation or left atrial appendage occlusion under uninterrupted anticoagulation: a multicentre experience on efficacy and complications.* Europace, 2019. **21**(7): p. 1048-1054.

4. Sekhar, A., et al., *Femoral arterial closure using ProGlide(R) is more efficacious and cost-effective when ambulating early following cardiac catheterization.* Int J Cardiol Heart Vasc, 2016. **13**: p. 6-13.

APPENDIX I: ABBREVIATIONS AND ACRONYMS

Abbreviations	
ADE	Adverse Device Effect
AE	Adverse Event
AF	Atrial Fibrillation
ASD	Atrial Septal Defect
AV	Arteriovenous
CEC	Clinical Events Committee
CIP	Clinical Investigation Plan
COVID-19	Coronavirus Disease 2019
СТ	Computer Tomography
DMP	Data Management Plan
DUS	Duplex Ultrasound
eCRF	Electronic Case Report Form
EDC	Electronic Data Capture
F	French Size
FDA	Food and Drug Administration
Fo8	Figure of 8
FU	Follow-up
HIPAA	Health Insurance Portability and Accountability Act
ICF	Informed Consent For
IRB	Institutional Review Board
ITT	Intent-to-treat
MC	Manual Compression
PPG	Product Performance Group
SAE	Serious Adverse Event
SMC	Suture-Mediated Closure (and Repair) System
US	United States
USADE	Unanticipated Serious Adverse Device Effect

APPENDIX II: DEFINITIONS

DUS-detected Vascular Complication Definitions

Hematoma - A collection of blood outside of the blood vessel. Characterized on ultrasound by a hypoechoic region adjacent to the blood vessel with no flow on doppler interrogation.

Pseudoaneurysm - A blood vessel abnormality resembling an aneurysm (localized abnormal dilatation of a blood vessel) but consisting of a collection of blood with persistent flow outside an artery, contained by surrounding tissue and due to a leaking hole through all layers of the arterial wall. The leaking hole is due to injury of (e.g., rupture of or trauma to) the arterial wall, and is related to the access site

DVT (Deep Venous Thrombosis) - Clot in the deep venous system. The age of the clot is categorized as Acute, Age-Indeterminate or Chronic.

Acute:

Homogenous hypoechoic thrombus. Thrombus poorly organized. Dilated vein wall (if occluded). Edema surrounding vessel wall. **Age Indeterminate:** Shares characteristics of acute and chronic thrombus. Lightly echogenic thrombus. Less organized thrombus. Vein wall appearing close to normal in size. Partially compressible. **Chronic:** Hyperechoic thrombus. Thrombus well organized with well-defined borders. Thrombus attached to vessel walls.

Collaterals may be present.

AV (Arterio-Venous) Fistula - an abnormal narrow connection between an artery and vein. The doppler characteristics include high turbulence within the fistula and arterialized/ pulsatile flow in the vein cephalad to the fistula. The artery may demonstrate a low resistive flow cephalad to the fistula tract.

Dissection - A tear of the vessel wall that allows blood to separate the intima and media from the externa. This appears a hyperechoic line within the vessel. Doppler

Clinical Investigation Plan

flow within the dissection depends on the extent of the dissection flap. It may range from a to-and-fro pattern to complete occlusion of the involved vessel.

A complete perforation on duplex ultrasound - a visible jet of color doppler traveling through the vessel wall resulting in a non-organized anechoic or heterogenous collection outside of the vessel that is actively increasing in size.

A complete tear on duplex ultrasound - a combined dissection/perforation duplex appearance with a jet of color doppler traveling through the vessel wall resulting in a non-organized anechoic or heterogenous collection outside of the vessel actively increasing in size, as well as possible visibility of a linear echogenic structure visible within the vessel lumen.

Other Access Site Related Complications

Access site-related nerve injury - Dysfunction with a loss of movement or sensation in parts of the legs due to damage to the femoral nerve. It may be caused by direct injury (trauma), prolonged pressure on the nerve compression, stretching, or entrapment of the nerve.

Infection - The invasion and growth of germs in the body. The germs may be bacteria, viruses, yeast, fungi, or other microorganisms. Infections can begin anywhere in the body and may spread all through it. An infection can cause fever and other health problems, depending on where it occurs in the body.

Pulmonary embolism - A pulmonary embolism (PE) is a sudden blockage in a pulmonary artery by a substance that has moved from elsewhere in the body through the bloodstream. DVT is the main cause of PE.

Venous access site injury including vessel laceration - Access site injury is defined as any untoward harm associated with a therapeutic or diagnostic health care intervention. Vessel laceration is defined as a tear in tissue caused by a shearing or crushing force.

Venous bleeding, retroperitoneal bleeding - Venous bleeding is defined as a continuous blood flow from a vein. Venous bleeding is less severe than arterial bleeding, but it can still be life threatening. Retroperitoneal bleeding is defined as bleeding into the retroperitoneal space.

Clinical Investigation Plan

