4.0 ENDPOINTS

4.1 Primary Endpoints and Rationale

The primary endpoint of this study is:

• Vascular complications detected by scheduled DUS at discharge or 30 days in asymptomatic/non-visible complication subjects

In real-world practice, femoral DUS is not routinely done in ablation procedures and only done when access site-related complications are visible (such as hematomas) and/or symptomatic. Therefore, a scheduled femoral DUS in asymptomatic or non-visible complication subjects will support the overall safety of Perclose SMC in multiple access site closures in a single vein. Any visible and/or symptomatic access site-related complications will be also be captured but will be excluded from the primary endpoint analysis.

The primary endpoint is further categorized as major or minor. Major complications are defined as those which require surgical, interventional, or pre-specified repair and/or hospitalization. All other complications are considered to be minor complications.

Vascular access site-related complications include, but are not limited to:

- Femoral vein stenosis (> 50%) development at the puncture site related to closure technique
 - Requiring surgical or percutaneous repair (major)
 - Not requiring surgical or percutaneous repair
- Deep vein thrombosis in the target limb
 - Requiring surgical or percutaneous repair (major)
 - Not requiring surgical or percutaneous repair

Study Name: Perclose Multi-Access DUS Trial

- Venous bleeding, retroperitoneal bleeding
 - Requiring surgical or percutaneous repair (major)
 - o Not requiring surgical or percutaneous repair
- Venous access site injury including vessel laceration
 - Requiring surgical repair, angioplasty, stenting, ultrasound-guided compression, or thrombin injection (major)
 - Not requiring above
- Re-bleeding at the access site
 - Requiring treatment or re-hospitalization (major)
 - Not requiring treatment or re-hospitalization
- Hematoma
 - Hematoma \geq 6 cm
 - Requiring surgical or percutaneous repair (major)
 - Not requiring surgical or percutaneous repair
- Pseudoaneurysm
 - Requiring surgical or percutaneous repair (major)
 - Requiring thrombin injection, fibrin adhesive injection, or ultrasound-guided compression (major)
 - Not requiring above
- Arteriovenous (AV) fistula
- Venous tear
 - Requing surgical or percutaneous repair (major)
 - Not requiring surgical or percutaneous repair
- Venous perforation
 - Requiring surgical or percutaneous repair (major)

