 - Not requiring surgical or percutaneous repair
- Arterial tear
 - Requiring surgical or percutaneous repair (major)
 - o Not requiring surgical or percutaneous repair
- Arterial perforation
 - Requiring surgical or percutaneous repair (major)
 - Not requiring surgical or percutaneous repair

• Other Complications found by DUS

DUS images will be analyzed by the independent DUS core laboratory and used for the primary endpoint analysis (**complications with bold face**). Investigators are also required to assess DUS detected complications, but the core laboratory is blinded to the site's assessment.

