6.4 Discharge (Complication Assessment)

At the time of discharge, the investigator should assess whether the subject has symptomatic or visible access site complications. In addition, femoral DUS must be done per the Corelab Guideline in the leg or legs in which access sites were closed in all subjects registered in this study to detect asymptomatic/non-visible complications if they exist. If a complication is treated, it should also be recorded in the eCRF.

DUS images should be uploaded for Corelab analysis per Abbott's specified method within 7 days from the procedure. The core laboratory will review the images and provide their assessment to investigators to determine whether 30-day DUS is required.

The investigator should record:

- Time of DUS
- Time of Discharge

Study Name: Perclose Multi-Access DUS Trial

Clinical Investigation Plan

Access site complications:

- Femoral vein stenosis (> 50%) development at the puncture site related to closure technique
 - Requiring surgical or percutaneous repair
 - Not requiring surgical or percutaneous repair
- Deep vein thrombosis in the target limb
 - Requiring surgical or percutaneous repair
 - Not requiring surgical or percutaneous repair
- Venous bleeding, retroperitoneal bleeding
 - Requiring surgical or percutaneous repair
 - Not requiring surgical or percutaneous repair
- Venous access site injury including vessel laceration
 - Requiring surgical repair, angioplasty, stenting, ultrasound-guided compression or thrombin injection
 - Not requiring above
- Re-bleeding at the access site
 - Requiring treatment or re-hospitalization
 - Not requiring treatment or re-hospitalization
- Hematoma
 - Requiring surgical or percutaneous repair
 - Hematoma \geq 6 cm but not requiring transfusion or surgical intervention
 - None of above
- Pseudoaneurysm
 - Requiring surgical or percutaneous repair
 - Requiring thrombin injection, fibrin adhesive injection, or ultrasound-guided compression
 - Not requiring above
- AV fistula
 - Requiring surgical or percutaneous repair
 - Not requiring surgical or percutaneous repair
- Venous tear
 - Requiring surgical or percutaneous repair (major)
 - Not requiring surgical or percutaneous repair

- Venous perforation
 - Requiring surgical or percutaneous repair (major)
 - Not requiring surgical or percutaneous repair
- Arterial tear
 - Requiring surgical or percutaneous repair (major)
 - Not requiring surgical or percutaneous repair
- Arterial perforation

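### The discharge classes file a large transfused hematoma with trivial ones; separately, the visible text does not settle whether a silent hematoma below 6 cm counts in the primary endpoint

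*Combined protocol and SAP*

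**What the plan says.** Hematoma appears in four places in the plan.

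- **Section 4.1 (primary endpoint).** Under the hematoma entry stand a line reading "Hematoma \geq 6 cm", a line for cases needing repair (major) and a line for cases not needing it. No line covers smaller hematomas. The list is open ("Vascular access site-related complications include, but are not limited to") and ends with the entry "Other Complications found by DUS". Major means needing repair or hospitalization; for the rest, "All other complications are considered to be minor complications". The primary analysis uses the core laboratory's reading of the items set in bold face, and visible or symptomatic complications are excluded from it.
- **Section 4.2 (descriptive endpoints).** Hematoma is listed without a size.
- **Section 6.4 (discharge assessment).** The investigator's form has three hematoma classes: repair needed; at least 6 cm "but not requiring transfusion or surgical intervention"; and everything else.
- **Appendix II (DUS-detected definitions).** Hematoma is "A collection of blood outside of the blood vessel", followed by its ultrasound appearance. No minimum size is given.

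**The concern.** The two points have different consequences and should be kept apart.

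**Severity classes.** The three classes in Section 6.4 look like a descending scale, but the middle one carries a no-transfusion condition that no other class picks up. A large hematoma that needs transfusion therefore drops past the middle class into the lowest one. A table built from these classes would show one of the more serious unrepaired hematomas as one of the least serious.

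**Size rule for the primary count.** The study exists to find complications that only a scheduled DUS would show. A small perivascular collection is a plausible finding of that kind, so whether it counts may matter to the reported rate. Conduct is touched as well. A vascular complication on the discharge DUS triggers a 30-day site visit and repeat DUS (Sections 6.5 and 6.7), and every vascular complication must be recorded as an adverse event (Section 7.0). If readers differ on whether a small collection is a complication, follow-up imaging could differ between similar subjects.

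**Working it through.** The plan states no hematoma rate, power or test, so there is no figure of its own to reproduce.

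**Step 1: the Section 6.4 classes.** Cross size (at least 6 cm, below 6 cm) with repair (yes, no) and transfusion (yes, no), and read off the class:

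| Size | Repair | Transfusion | Class in 6.4 | Repair-based grade in 4.1 |
|---|---|---|---|---|
| any | yes | any | repair | major |
| ≥6 cm | no | no | middle class | not repair |
| ≥6 cm | no | yes | **residual** | not repair |
| <6 cm | no | no | **residual** | not repair |
| <6 cm | no | yes | residual | not repair |

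The third and fourth rows share a class although they differ in both size and treatment. Every row is still a hematoma, and the repair class in 6.4 matches the repair-based major grade in 4.1 throughout. Reclassifying the third row therefore changes the number of hematomas, and the primary count, by 0. One limit of this check is that 4.1 also makes hospitalization a major criterion, which the 6.4 hematoma classes do not record.

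**Step 2: the size rule.** Two readings of Section 4.1 fit the visible text:

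- *Entry reading:* only hematomas of 6 cm or more belong to the primary list.
- *Grading reading:* any hematoma belongs, and 6 cm is one descriptive line under it.

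The open list, the closing catch-all entry, the rule that all else is minor, and the absence of a size in 4.2 and Appendix II favour grading. The presence of a 6 cm line with no counterpart below it favours entry. The indentation of the bullets and the bold face that marks primary items would help to decide, but neither is visible in the text available here.

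**Step 3: what the choice could be worth.** Inputs: n = 35 registered subjects (Section 5.6), and k = the number of subjects whose only finding is a silent hematoma below 6 cm. The value of k is an assumption. With no other events, the entry reading gives 0/35 and the grading reading gives k/35. Intervals are Clopper-Pearson 95%.

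| k | Entry reading | Grading reading |
|---|---|---|
| 1 | 0% (0-10.0) | 1/35 = 2.9% (0.1-14.9) |
| 3 | 0% (0-10.0) | 3/35 = 8.6% (1.8-23.1) |
| 5 | 0% (0-10.0) | 5/35 = 14.3% (4.8-30.3) |
| 10 | 0% (0-10.0) | 10/35 = 28.6% (14.6-46.3) |

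Excluding visible or symptomatic complications may shrink the denominator. At n = 30, also an assumption, one subject is worth 1/30 = 3.3 points, and five give 16.7% (5.6-34.7) against 0% (0-11.6).

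The chance that the two readings differ by at least one subject is 1 - (1 - p)^35 for an assumed rate p of such subjects: 51% at p = 2%, 83% at 5%, 97% at 10%, and above 99% at 20%.

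**The case against.** A reader might infer more than the documents support, in four ways.

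- **That the 6.4 gap makes the primary count unstable.** It does not. The 6.4 classes are the investigator's grading, whereas the primary count comes from the core laboratory's reading, and any 6.4 class is still a hematoma. A hematoma needing transfusion would probably also be visible or symptomatic (an inference), and so outside the primary analysis.
- **That a serious unrepaired hematoma would be lost.** Section 6.4 asks for treatment of a complication to be recorded, Sections 7.0 and 7.3.1 require every vascular complication to be reported as an adverse event, and the events committee adjudicates the Section 4.2 events (Section 10.8). The case is mislabelled in one list, but it can be found elsewhere.
- **That Section 4.1 sets a 6 cm entry threshold and so contradicts Appendix II.** This is only one reading, and most of the visible wording leans the other way. The original bold face and indentation may decide it.
- **That the core laboratory applies Appendix II.** No section says so. Section 6.4 cites a Corelab Guideline that is not in the public text and may contain a size rule.

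It is also fair to say that the rates in Step 3 are invented for illustration, that no hypothesis test or success criterion depends on them (Sections 8.6 and 8.7), and that Section 4.2 already provides for hematoma without a size limit in the descriptive results.

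All of this stands, and it limits the point. It leaves untouched the faulty 6.4 classes, which do not depend on formatting, and the lack of a plain statement of what the 6 cm line does.

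**Conclusion.** Both points hold as matters of wording to be clarified. The Section 6.4 classes are wrong as written: a hematoma of 6 cm or more with transfusion and no repair shares a class with the smallest collections. The effect is on severity reporting, with no change to the primary count.

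The size rule is unsettled in the visible text rather than shown to be contradictory. If silent hematomas below 6 cm occur, each one in a subject with no other finding moves the primary rate by 2.9 points at n = 35. The number of such subjects is unknown, so the possible shift runs from nothing to several times that. No formal decision turns on it, but in a descriptive study the rate is the result, so it should not depend on an unstated rule.

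**What to change.** 1. In Section 6.4, replace the hematoma classes with three that are exclusive and complete: repair; 6 cm or more without repair; below 6 cm without repair. Record transfusion as a separate yes/no item.
2. In Section 4.1 and Appendix II, state in the same words whether 6 cm is an entry criterion for the primary endpoint or only a grading criterion. If the Corelab Guideline already has a rule, bring it into the plan.
3. Report the primary rate twice: with all core-laboratory hematomas, and with only those of 6 cm or more. This needs the core laboratory to record each hematoma's size, or at least which side of 6 cm it falls on.

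The cost is a change to eCRF wording and one extra table row. The downside for the sponsor is that the all-size rate may look less favourable. These are changes to recording and reporting only; clinical management is not affected.
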